### 8.8.2 Definition of Dose Limiting Toxicity

A DLT is defined as the occurrence of any of the following TEAEs that occur despite optimal medical management, graded using NCI-CTCAE, v 5.0 during Cycle 1; except those that are clearly and incontrovertibly due to disease progression or extraneous causes.

- Any death not clearly due to the underlying disease or extraneous causes.
- Grade  $\geq 3$  non-hematologic toxicity (unless otherwise noted below).
- Grade  $\geq 3$  nausea and/or vomiting and/or Grade 3 diarrhea not resolving within 72 hours with optimal treatment.
- Grade 3 neutropenia accompanied with fever and/or infection.
- Grade 3 thrombocytopenia associated with bleeding.

- Grade  $\geq 4$  hematologic toxicity.
- AST or ALT  $> 3\times$  the ULN and a total bilirubin  $> 2\times$  the ULN without initial findings of cholestasis (elevated serum alkaline phosphatase) and no other reason for the increase in transaminases and total bilirubin.
- AST or ALT  $> 8\times$  ULN or AST or ALT  $> 5\times$  ULN for  $\geq 14$  days.
- ALT or AST  $> 3\times$  ULN with the appearance of fatigue, nausea, vomiting, right upper quadrant pain or tenderness, fever, rash, and/or eosinophilia ( $>5\%$ ).
- Grade  $\geq 3$  blurred vision or retinopathy.
- Grade  $\geq 3$  fatigue that does NOT resolve to Grade  $\leq 1$  within 7 days.
- Grade  $\geq 2$  TEAEs that result in omission of treatment for  $\geq 7$  days during Cycle 1 or delay of Cycle 2 for  $\geq 7$  days.
- Multiple concurrent AEs in the same subject leading to DLT will be considered a single DLT.

Subjects in Part A (Dose Escalation) who are not DLT evaluable may be replaced as appropriate. DLT evaluable is defined as experienced a DLT and/or received at least 75% of the originally assigned doses in the first cycle. Subjects receiving less than 75% of the planned dose in Cycle 1 without a DLT will be evaluated in the overall safety analysis, but not for the purposes of dose escalation.

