#### **8.10 Dose Modification for Phase I and Phase II**

All AEs should be assessed according to the NCI-CTCAE, v 5.0. In the event of multiple toxicities, dose delays and modifications should occur in accordance with the highest grade AEs observed.

Institutional guidelines should be followed in the event of hypersensitivity reaction.

Subjects who experience a DLT or any of the following AEs in Cycle 2 and beyond will have study drug treatment interrupted. Dose modification will be allowed as per [Table 8](#). Modified dose levels are shown in [Table 9](#).

Dose Modification Guidelines for Intermediate Doses are presented in [Table 10](#). The first dose reduction will be approximately 20% to 30%, the second dose reduction is

approximately 40% to 50%, and the third dose reduction is approximately 70% to 80%. Dose reductions below 15 mg daily are not allowed.

Dose modifications will only be made for TEAEs that are not clearly due to disease progression or extraneous causes.

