**Table 8: Dose Modification or Treatment Delay for OP-1250-Related Treatment-Emergent Adverse Events**

Worst toxicity NCI-CTCAE, v5.0 a Grade (v5.0)	Recommended dose modifications for OP-1250
Blood	
Febrile Neutropenia Grade 3	
 
Hold OP-1250 until ANC is <math>\geq 1.0 \times 10^9/\text{L}</math> or baseline. If treatment delay is <math>\leq 14</math> days, restart at 1 dose level lower.
 
If treatment delay is <math>> 14</math> days, discontinue treatment.
 

Febrile Neutropenia Grade 4	
 
Discontinue treatment.
 

Investigations	
Neutropenia (ANC/neutrophils decreased)	
Grade 3 (ANC $< 1.0\text{--}0.5 \times 10^9/\text{L}$ )	
 
Hold OP-1250 until ANC is <math>\geq 1.0 \times 10^9/\text{L}</math> or baseline. If treatment delay is <math>\leq 7</math> days, restart at same dose.
 
If treatment delay is <math>> 7</math> but <math>\leq 21</math> days, restart 1 dose level lower.
 
If treatment delay is <math>> 21</math> days, discontinue treatment.
 

Grade 4 (ANC $< 0.5 \times 10^9/\text{L}$ )	
 
Hold OP-1250 until ANC is <math>\geq 1.0 \times 10^9/\text{L}</math> or baseline. If treatment delay is <math>\leq 7</math> days, restart 1 dose level lower.
 
If treatment delay is <math>> 7</math> days, discontinue treatment.
 

Thrombocytopenia (platelet count decreased)	
Grade 3 (Platelets $< 25\text{--}50 \times 10^9/\text{L}$ ) without bleeding	
 
Hold OP-1250 until platelet count is <math>\geq 75 \times 10^9/\text{L}</math>. If treatment delay is <math>\leq 7</math> days, restart at same dose.
 
If treatment delay is <math>> 7</math> but <math>\leq 21</math> days, restart 1 dose level lower.
 
If treatment delay is <math>> 21</math> days, omit dose and discontinue treatment.
 

Grade 4 (Platelets $< 25 \times 10^9/\text{L}$ ) or Grade 3 with bleeding	
 
Hold OP-1250 until platelet count is <math>\geq 75 \times 10^9/\text{L}</math>. If treatment delay is <math>\leq 7</math> days, restart 1 dose level lower.
 
If treatment delay is <math>> 7</math> days, discontinue treatment.
 

Renal	
Serum creatinine	

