## 9 DEFINITION OF AN ADVERSE EVENT

An AE is any unfavorable and unintended sign, symptom, or disease temporally associated with the use of an investigational (medicinal) product or other protocol-imposed intervention, regardless of attribution. An AE may include inter-current illnesses or injuries that represent an exacerbation (increase in frequency, severity, or specificity) of pre-existing conditions (eg, worsening of asthma). Whenever possible, it is preferable to record a diagnosis as the AE term rather than a series of symptoms relating to a diagnosis. In NCI-CTCAE, v 5.0, unequivocal neoplastic disease progression is captured as the verbatim term of disease progression under the System Organ Class “General”. When an AE of disease progression meets the requirements to be considered serious, the verbatim term should be reported as disease progression and should not be reported as an SAE. Evidence that the AE or death was a manifestation of underlying disease (eg, radiological changes suggesting tumor growth or progression: clinical deterioration associated with a disease process) should be documented in the EDC.

The reporting period for AEs is the period from administration of the first dose of study drug through 30 days after the last administration of study drug. All related AEs will be followed to resolution, stabilization, or loss of contact with the subject. All unrelated AEs will be followed until the time of the Safety Follow-up visit, which is between 30 to 42 days after the EOT visit.

The investigator will assess AEs for severity, for relationship to IP, and whether the event meets 1 or more of the definitions of an SAE (see [Section 9.1](#)).

The investigator will determine the severity of each AE and will record it on the source documents and in the AE eCRF, using NCI-CTCAE, v 5.0.

The investigator will determine the relationship of an AE to the IP and will record it on the source documents and in the AE eCRF. All AEs should be considered related to the study drug unless such relationship can be definitely excluded.

In order to classify AEs and diseases, preferred terms will be assigned by the sponsor or its designee to the original terms entered in the eCRF, using MedDRA.

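### Table 8 gives conflicting actions when one febrile episode meets both a febrile neutropenia row and a neutropenia row of the same grade, and no written rule breaks the tie

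*Protocol*

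**What the plan says.** Protocol Section 8.10, Table 8, handles neutropenia in two places.

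- Under the Blood heading, "Febrile Neutropenia Grade 3" means holding OP-1250 until the ANC recovers to 1.0 × 10⁹/L or baseline. If the delay is at most 14 days the instruction ends "days, restart at 1 dose level lower"; beyond 14 days treatment is discontinued. "Febrile Neutropenia Grade 4" means discontinuation, with no delay condition.
- Under the Investigations heading, the rows titled "Neutropenia (ANC/neutrophils decreased") use the same recovery point. At Grade 3 (ANC 0.5 to below 1.0), a delay of at most 7 days ends "days, restart at same dose"; more than 7 and up to 21 days means one level lower; more than 21 days means discontinue. At Grade 4 (ANC below 0.5), a delay of at most 7 days means one level lower and a longer delay means discontinue.

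Section 8.10 gives one general rule for overlaps, repeated in substance in the Synopsis: "In the event of multiple toxicities, dose delays and modifications should occur in accordance with the highest grade AEs observed".

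Two other places bear on this. Section 8.8.2 lists "Grade 3 neutropenia accompanied with fever and/or infection" as a dose-limiting toxicity, so the protocol foresees a Grade 3 count together with fever. Section 9 tells sites that "it is preferable to record a diagnosis as the AE term rather than a series of symptoms relating to a diagnosis".

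**The concern.** An episode of febrile neutropenia also has a neutrophil count, so the same patient on the same day can satisfy a row under Blood and a row under Investigations. If those rows give different instructions and nothing ranks them, two sites can follow the table faithfully and one will re-dose where the other stops treatment.

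Neutropenia is the toxicity to which the protocol pays most attention. Section 6.7 reports 4 Grade 4 neutropenia events in Phase Ia and says blood counts were added because of them. Both AESI terms in Section 9.2 are Grade 4 neutrophil events. Table 8 is also binding in effect, because Section 8.11 ends treatment for an adverse event that requires discontinuation as set out there. On the analysis side, SAP Section 13.2 tabulates events leading to discontinuation, dose reduction or withheld drug by preferred term, and Section 13.3 summarises dose reductions and relative dose intensity. Uneven handling of like episodes would feed into those tables.

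**Working it through.** The plan states no figure to reproduce. The check sets the rows side by side by length of delay (FN = febrile neutropenia; ANC = neutrophil-count row), then applies the Section 8.10 rule.

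**Step 1. Each row as a function of delay**

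| Row | 1–7 days | 8–14 days | 15–21 days | >21 days |
|---|---|---|---|---|
| FN Grade 3 | 1 level lower | 1 level lower | discontinue | discontinue |
| ANC Grade 3 | same dose | 1 level lower | 1 level lower | discontinue |
| FN Grade 4 | discontinue | discontinue | discontinue | discontinue |
| ANC Grade 4 | 1 level lower | discontinue | discontinue | discontinue |

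**Step 2. Compare each FN row with each ANC row, and ask whether the highest-grade rule decides**

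| Pairing | Delays where the actions differ | Does the rule decide? |
|---|---|---|
| FN 3 / ANC 3 | 1–7 (lower vs same dose); 15–21 (discontinue vs restart lower) | No, equal grade |
| FN 4 / ANC 4 | 1–7 (discontinue vs restart lower) | No, equal grade |
| FN 3 / ANC 4 | 8–14 (restart lower vs discontinue) | Yes, ANC Grade 4 row, if both events are counted |
| FN 4 / ANC 3 | 1–7 (discontinue vs same dose); 8–21 (discontinue vs restart lower) | Yes, FN Grade 4 row, if both events are counted |

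All four pairings differ somewhere. The rule settles the two unequal-grade pairings and leaves the two equal-grade pairings open.

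**Step 3. Size of the open windows.** For Grade 3 in both, the rows differ over 7 + 7 = 14 of the first 21 possible delay lengths and agree at 8–14 and beyond 21 days. For Grade 4 in both, they differ over the first 7 and agree afterwards. These count delay lengths, not patients. As an illustration, for a Phase II subject started at 120 mg, Table 10 makes one level lower 90 mg. The Grade 3 conflict at 1–7 days is then between 120 mg and 90 mg, a difference of 30/120 = 25%.

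**Step 4. Is the overlap real?** For Grade 3 in both, yes: Section 8.8.2 names the combination. For Grade 4 in both, it is enough that a Grade 4 febrile episode can have ANC below 0.5. Table 8 gives no ANC range for either febrile row, and nothing in the documents excludes it.

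**Step 5. Is a limit implied by the table's own style?** The thrombocytopenia rows say explicitly whether they apply with or without bleeding. The neutropenia rows have no matching condition on fever, so as written they still apply when fever is present.

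**Step 6. The secondary case.** Assume that FN Grade 3 can include ANC below 0.5, for which the documents give no range. At delays of 8–14 days the febrile row says restart lower and the ANC Grade 4 row says discontinue. If both events are counted, Section 8.10 selects the Grade 4 row. If a site follows Section 9 and records only the febrile diagnosis, the documents do not say whether the count grade still enters the highest-grade rule.

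**The case against.** The best defence is that febrile neutropenia is a distinct and more specific condition with its own rows, so a different action for it is no contradiction. Reading the febrile row as the rule for febrile episodes gives one answer at every delay, and at equal grade that row is never the more lenient one. The reading is plausible but unwritten, and the bleeding distinction in the same table shows how it could have been written.

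Several stronger readings are tempting and do not hold.

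- A reader might infer that the whole block is unresolved. It is not: the highest-grade rule settles the unequal-grade pairings when both events are counted, including ANC 0.4 with fever and recovery on day 10.
- A reader might infer that the table tolerates a longer delay with fever (14 days) than without (7 days). That compares febrile Grade 3 with Grade 4 by count. At equal grade the discontinuation limit is 14 days with fever and 21 without at Grade 3; at Grade 4 it is immediate with fever and after 7 days without.
- A reader might infer that the action generally turns on the recorded term. The Section 8.10 rule speaks of events observed, Section 9's preference is for a diagnosis over symptoms, and Section 9.2 makes Grade 4 neutrophil events reportable within 24 hours. But Section 9.2 also asks for the most appropriate diagnosis, with laboratory values recorded where none can be established. Dependence on the term therefore remains possible, but only in the secondary case.
- A reader might infer that the choice of RP2D is compromised. Section 8.8.4 shows that 120 mg is already selected and reports no dose reductions or discontinuations due to an adverse event in the 37 Phase 1b patients reviewed.

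The documents report no febrile neutropenia event, and Table 8 heads its actions as recommended. Both temper the practical weight, but neither removes the conflict.

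**Conclusion.** The point holds for equal grades. Table 8 states opposing actions at Grade 3 for delays of 1–7 and 15–21 days, and at Grade 4 for delays of 1–7 days. The one written tie-breaker cannot choose between them. In two of these three windows the opposition is between stopping treatment and restarting it.

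The 8–14 day conflict between febrile Grade 3 and Grade 4 by count is secondary. It rests on the assumption that febrile Grade 3 can include ANC below 0.5, and it stays open only if the febrile term alone is recorded.

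How often this will matter cannot be estimated: the documents do not say how many of the 4 Grade 4 events in Phase Ia were febrile. What is exposed is subject safety and the comparability of the discontinuation, dose-reduction and exposure summaries. It is worth correcting because the conflict concerns the trial's main safety signal and costs little to remove.

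**What to change.** At the next amendment the sponsor should reconcile the febrile neutropenia rows, the neutropenia rows and the highest-grade rule in Section 8.10, and carry the result into the matching Synopsis text. Table 8 should state which row governs when one episode meets two rows, including two rows of equal grade. It should also say whether the neutropenia rows apply when fever is present, and whether the count grade still enters the highest-grade rule when only the febrile diagnosis is recorded under Section 9. Which delay limits and actions apply is for the sponsor's clinical team; none is proposed here.

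The cost is wording in Table 8 and Section 8.10, plus notice to sites. No extra subjects, visits or procedures are needed.

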Grade 3 ( $> 3.0\text{--}6.0 \times \text{ULN}$ )	
 
Hold OP-1250 until resolution to <math>\leq</math> Grade 1 or baseline, then restart 1 dose level lower.
 
If findings recur on 1 dose level lower, hold until resolves to <math>\leq</math> Grade 1 or baseline and restart at 2 dose levels lower. If findings recur, discontinue treatment.
 

Grade 4 ( $> 6.0 \times \text{ULN}$ )	
 
Discontinue treatment.
 

Hepaticb	
Grade 3 bilirubin increase	
 
Hold OP-1250 until resolution to <math>\leq</math> Grade 1 and restart 1 dose level lower.
 
If findings recur on 1 dose level lower, hold until resolves to <math>\leq</math> Grade 1 or baseline and restart at 2 dose levels lower. If findings
 

Worst toxicity NCI-CTCAE, v5.0 a Grade (v5.0)	Recommended dose modifications for OP-1250
	recur, discontinue treatment.
ALT or AST > 3× with concurrent > 2× ULN (or baseline) direct or total bilirubin For subjects with hepatic metastases, AST or ALT > 8× ULN or AST or ALT > 5× ULN for ≥ 14 days	
 
Hold OP-1250 until resolution to ≤ Grade 1 and restart 1 dose level lower.
 
If findings recur, discontinue treatment.
 

Grade 4 AST or ALT	
 
Discontinue treatment.
 

ALT or AST > 3× ULN with the appearance of fatigue, nausea, vomiting, right upper quadrant pain or tenderness, fever, rash, and/or eosinophilia (>5%)	
 
Discontinue treatment.
 

Gastrointestinal Toxicity	
Grade ≥ 3 nausea and/or vomiting and/or Grade 3 diarrhea not resolving within 72 hours with optimal treatment	
 
Hold OP-1250 until resolution to ≤ Grade 1 or baseline and restart 1 dose level lower.
 
If findings recur on 1 dose level lower, hold until resolves to ≤ Grade 1 or baseline and restart at 2 dose levels lower than original dose.
 
If findings recur on 1 dose level lower, hold until resolves to ≤ Grade 1 or baseline and restart at 3 dose levels lower than original dose.
 
If findings recur, discontinue treatment.
 

Cardiac	

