Grade 2 Sinus bradycardia	
 
Hold OP-1250 until resolution to ≤ Grade 1 or baseline and restart 1 dose level lower.
 
If findings recur on 1 dose level lower, hold until resolves to ≤ Grade 1 or baseline and restart at 2 dose levels lower than original dose.
 
If findings recur on 1 dose level lower, hold until resolves to ≤ Grade 1 or baseline and restart at 3 dose levels lower than original dose.
 
If findings recur, discontinue treatment.
 

Grade ≥ 3 Sinus bradycardia	
 
Discontinue treatment.
 

Grade 3 QTc prolongation	
 
Hold OP-1250; address any serum electrolyte abnormalities.
 
Upon resolution of QTcF to ≤ 500 msec, resume OP-1250 at 1 dose level lower.
 
If findings recur, discontinue treatment.
 

Grade 4 QTc prolongation	
 
Discontinue treatment.
 

Worst toxicity NCI-CTCAE, v5.0 a Grade (v5.0)	Recommended dose modifications for OP-1250
Eye Toxicity	
Grade 2 without changes in visual acuity	
 
• Hold OP-1250, contact Medical Monitor, and have ophthalmologist examination. If no concerning findings suggestive of drug effect and resolved to a <math>\leq</math> Grade 1 restart at 1 dose level lower.
 
• If it recurs, hold OP-1250 and contact Medical Monitor. If resolved to a <math>\leq</math> Grade 1, restart at 2 dose levels lower than original dose.
 
• If it recurs again, hold OP-1250 and contact Medical Monitor. If resolved to a <math>\leq</math> Grade 1, restart at 3 dose levels lower than original dose.
 

Grade 2 with changes in visual acuity Grade 3 or 4	
 
• Discontinue treatment.
 

Neurologic Toxicity	
Grade 2 Headache	
 
• If AE occurs that is not relieved with supportive care for 7 days the investigator or designee can reduce 1 dose level.
 
• If AE occurs that is not relieved with supportive care for 7 days the investigator or designee can reduce 1 additional dose level.
 
• If AE occurs that is not relieved with supportive care for 7 days the investigator or designee can reduce 1 additional dose level.
 

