### 8.11 Treatment Duration

In the absence of unacceptable OP-1250 treatment-related toxicity or disease progression, subjects may receive OP-1250 treatment for up to 1 year and beyond 1 year with the agreement of the investigator or designee and the sponsor.

Treatment will continue until any 1 of the following occurs:

- SAE or AE that requires dose discontinuation as described in [Section 8.10, Table 8](#).
- Progressive disease as determined by RECIST 1.1 (see [Appendix E](#)) (Tumor marker elevations in the absence of unequivocal radiologic progression of target or non-target lesions is not considered disease progression. Per RECIST 1.1, disease progression requires an overall disease burden increase based on the change in non-measurable disease that is comparable in magnitude to the increase that would be required to declare PD for measurable disease: ie, an increase in tumor burden representing an additional 73% increase in 'volume,' which is equivalent to a 20% increase in diameter in a measurable lesion.)
- Initiation of non-protocol anticancer therapy.
- Illness or condition that may interfere with the subject's participation or require treatment discontinuation.
- Treating investigator or designee's determination that continuation of protocol therapy is not in the subject's best interests.
- Pregnancy.
- Noncompliance.
- Voluntary withdrawal of consent.
- Sponsor termination of the study.

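### Eight rows of protocol Table 8 give two different restart doses for the same recurrence, and never name recurrence at the second reduced dose

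*Protocol*

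**What the plan says.** Eight rows of Table 8 share the same four-bullet structure:

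- gastrointestinal toxicity (nausea and vomiting at Grade 3 or above, Grade 3 diarrhea)
- Grade 2 sinus bradycardia
- Grade 3 headache
- Grade 3 dizziness
- other neurologic toxicity, Grade 3
- Grade 3 confusion
- other psychiatric toxicity, Grade 3
- other non-hematologic toxicity, Grade 3

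Bullet 1 holds the drug and restarts one level down. Bullet 2 says "If findings recur on 1 dose level lower, hold until resolves to \leq Grade 1 or baseline and restart at 2 dose levels lower" than the original dose. Bullet 3 says "If findings recur on 1 dose level lower, hold until resolves to ≤ Grade 1 or baseline and restart at 3 dose levels lower" than the original dose. Bullet 4 discontinues if findings recur, without naming a dose level.

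Other rows of the table handle repeat events without this duplication. Grade 3 creatinine and Grade 3 bilirubin end after two levels ("restart at 2 dose levels lower. If findings recur, discontinue treatment"). The Grade 2 eye row separates the second recurrence from the first ("If it recurs again, hold OP-1250 and contact Medical Monitor"). The Grade 2 headache row repeats one trigger, but its action is cumulative: "If AE occurs that is not relieved with supportive care for 7 days the investigator or designee can reduce 1 additional dose level".

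The text of Section 8.10 describes three successive reductions, the last worded as "the third dose reduction is approximately 70% to 80" percent, and sets a floor: "Dose reductions below 15 mg daily are not allowed". The Synopsis repeats both. Table 10 (Part B and Phase II) lists up to three reduced doses for each starting dose. Table 9 (Part A) lists only two, and its second reduction from 30 mg is 15 mg on alternate days.

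**The concern.** Two bullets with the same condition and different actions cannot both be followed. Read literally, a subject whose toxicity returns on the first reduced dose should restart at both the second and the third reduced dose. A subject whose toxicity returns on the second reduced dose meets neither trigger and falls through to the discontinuation bullet.

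This is operative text. Section 8.11 ends treatment for an "SAE or AE that requires dose discontinuation as described in" Table 8, and Section 8.3.3 relies on the same table when it defines unacceptable toxicity. A site that follows the words could skip a dose level or take a subject off treatment one step early. SAP Section 9.2 lists receipt of an incorrect dose as a possible important protocol deviation, and here the wording alone does not say which dose is the incorrect one.

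Separately, the alternate-day cell in Table 9 conflicts with the floor in Section 8.10.

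**Working it through.** The plan gives no figure to reproduce. The check is a row-by-row reading followed by a look-up of doses.

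**1. Count of rows.** Rows of Table 8 in which bullets 2 and 3 share the trigger but differ in restart level: 8. Of these, rows that name recurrence at 2 levels lower: 0.

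**2. Where the levels are counted from.** Bullet 1 restarts one level down from the starting dose, and bullets 2 and 3 state their restart levels relative to the original dose. The creatinine and bilirubin rows use the same trigger phrase for the first recurrence only. Recurrence one level lower therefore means recurrence on the first reduced dose.

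**3. Dose consequences.** Inputs are the reduced doses in Table 10 (mg daily). The gap is 1 − (third reduced dose ÷ second reduced dose).

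| Start | First | Second | Third | Recurrence on first reduced dose: bullet 2 vs bullet 3 | Gap |
|---|---|---|---|---|---|
| 120 | 90 | 75 | 45 | 75 vs 45 | 1 − 45/75 = 40% |
| 90 | 75 | 60 | 30 | 60 vs 30 | 1 − 30/60 = 50% |
| 75 | 60 | 45 | 30 | 45 vs 30 | 1 − 30/45 = 33% |
| 60 | 45 | 30 | 15 | 30 vs 15 | 1 − 15/30 = 50% |

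Starts of 45 and 30 mg have no third reduction in Table 10, so bullet 3 has no dose to point to.

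**4. The ladder from 120 mg.**

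- Intended: 90, then 75, then 45 mg, then stop.
- Literal: recurrence on 90 mg gives 75 mg and 45 mg together. Recurrence on 75 mg is covered only by bullet 4, which means stop, although Table 10 provides 45 mg.

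**5. Table 9.** 15 mg on alternate days averages 15 ÷ 2 = 7.5 mg per day, and 7.5 ÷ 15 = 50% of the floor. Table 10 marks the same step (second reduction from 30 mg) as not applicable. Table 9 has no third-reduction column, although Table 8 calls for restarts three levels down. At 30 and 60 mg that column would be empty anyway, because the first or second reduction already reaches 15 mg daily. The gap therefore concerns Part A starts of 120 mg and above.

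**The case against.** The best defence is that the trigger is relative: one level lower than the dose most recently taken. Bullet 2 would then be the first recurrence and bullet 3 the second, with no clash, much as the Grade 2 rows repeat one trigger for successive steps. This does not rescue the wording. The surrounding bullets count levels from the original dose. The Grade 2 rows work only because their action is an additional level, and the eye row shows how the protocol words a second recurrence when it means one.

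Other parts of the defence stand:

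- **Intent.** It can be inferred from the bullet order, the eye row, the third reduction in Section 8.10 and Table 10. A site would have to overlook all of these to misdose.
- **Status of the tables.** Table 8 is headed as recommendations, and Tables 9 and 10 are titled guidelines. Sections 8.3.3 and 8.11 nevertheless use Table 8 for decisions to stop treatment.
- **Reach.** Section 8.8.4 reports no dose reductions or discontinuations due to an adverse event among 37 Phase 1b patients at 60 or 120 mg. These are interim data with no stated follow-up, but they suggest that few subjects will reach a recurrence after a reduction.
- **Starting doses.** The documented Part B and Phase II starts are 60 and 120 mg, for which the gaps are 50% and 40%. The 33% comes only from a 75 mg start, and no document reports a subject starting there.
- **Table 9.** Escalation is complete (Section 6.5.2). The faulty cell concerns only subjects who started at 30 mg and need a second reduction, and active Phase I subjects may be treated at the recommended dose with Medical Monitor approval (Section 8.8.4).

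**Conclusion.** The point holds and is minor. Bullet 3 is wrong as written in eight rows: it duplicates bullet 2's trigger with a different restart dose, and recurrence on the second reduced dose is left to the stopping bullet. For the four Table 10 starts with a third reduction, bullet 3's dose is 33% to 50% below bullet 2's (40% at the recommended dose of 120 mg). The Table 9 cell averages half the permitted floor.

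This rests on counting dose levels from the original dose, as the neighbouring bullets do, and on Table 10 governing the doses. How often the situation will arise cannot be derived from the documents and is not estimated here. No endpoint, sample size or analysis is affected.

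**What to change.** - **Bullet 3, all eight rows:** change the trigger to *If findings recur on 2 dose levels lower*.
- **Last bullet, same rows:** keep it as a catch-all, for example *If findings recur again, or no lower dose level is available, discontinue treatment*. This covers the 45 and 30 mg starts in Table 10 and Part A subjects on the last dose listed in Table 9.
- **Table 9, second reduction from 30 mg:** replace the alternate-day dose with *not applicable*.
- **Sites:** send a short clarification.

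The cost is one phrase and a short addition in each of eight rows, one table cell and a note to sites. The intended dose ladder stays as it is.
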